5 STUDY POPULATION CHARACTERISTICS

5.1 Subject disposition

The number of subjects who were enrolled, dosed, subjects included in each analysis set, and subjects who completed or prematurely discontinued the study, as well as the reason for discontinuation, will be presented by dose arm and overall. Screen failure reasons will be summarized, based on the ES.

In addition, the following listings will be presented by dose arm:

- Subject disposition (ES)
- Study discontinuation (SS)
- Visit dates (SS)
- Subject analysis sets (ES)

The listing of subject disposition will include the date of informed consent, date of genomic consent (if applicable), date of randomization (if applicable), date and time of first and last dose of UCB7665 (if applicable), date of premature termination and primary reason (if applicable) and date of final contact.

The listing of study discontinuation will include the reason for discontinuation and the number of days on UCB7665.

The number of days on UCB7665 will be calculated as follows:

Number of days on UCB7665 = [(Date of Last Dose Received) – (Date of First Dose Received)] + 1

5.2 Protocol deviations

Important protocol deviations will be identified and classified by the deviation types identified in the important protocol deviations document. A listing of all important protocol deviations identified at the DEM will be presented for all subjects in the SS, and will include the deviation type and description. The number and percentage of subjects in the SS with important protocol deviations will be summarized by dose arm and overall. The denominator for percentages will be the number of subjects in the SS.

6 DEMOGRAPHICS AND OTHER BASELINE CHARACTERISTICS

6.1 Demographics

A by-subject listing of Baseline demographics will be presented by dose arm for the ES. This will include the year of birth (if available), age (in years), sex, race, ethnicity, height (in cm), weight (in kg) and body mass index (BMI). The age will be directly entered into the study database and will not be re-calculated for the statistical analysis.

BMI in kg/m^2 is calculated based on the height (in m) and the weight (in kg) using the following formula:

$$\text{BMI (kg/m}^2\text{)} = \text{weight (kg)} / [\text{height (m)}]^2$$

BMI will be reported to 1 decimal place.

All Baseline demographic characteristics (with the exception of year of birth) will be summarized by dose arm and overall for the SS. Number and percentage of patients with a BMI equal or higher than 30 will also be summarized by dose arm.

The summary of age will include descriptive statistics and categorical summaries, the latter based on requirements for EudraCT and clinicaltrials.gov reporting.

For the EudraCT reporting, the categories will include:

- 18 to <65 years
- 65 to <85 years
- ≥ 85 years

For the clinicaltrials.gov reporting, the categories will include:

- ≤ 18 years
- 19 to <65 years
- ≥ 65 years

Childbearing potential will be listed for the SS.

6.2 Other Baseline characteristics

Baseline disease characteristics will be listed and summarized by dose arm for the SS including the following:

- Duration of disease
- Karnofsky Performance Scale Index
- ITP bleeding scale (skin, visible mucosae and organs, with gradation of severity [SMOG])
- ITP-specific autoantibodies [REDACTED] expressed in terms of optical density (OD) for MAIPA analysis and pre-chloroquine minus post chloroquine treated scores for PIFT

- Immunological variables (IgG [including total IgG and IgG subclasses measured by ACM Global Central Laboratory], IgM, IgA, IgE and lymphocytes [B and T])
- Serum (C3 and C4) and plasma complement levels (C3a and C5a)
- Platelet count (measured by ACM Global Central Laboratory)
- Number of prior ITP medications received
- Number of prior ITP medications received categorized
- Prior ITP medications received by preferred term
- Medical history of splenectomy (MedDRA v20.2, Preferred Term="Splenectomy")

The duration of disease will be calculated as follows, where the date of diagnosis will be obtained from the ITP history page of the case report form (CRF):

$$\text{Duration (years)} = (\text{Date of Screening} - \text{Date of Diagnosis})$$

If the date of diagnosis is missing, the duration of disease will not be calculated. In the case of the start day being missing, the day will be imputed with the 1st of the month in the calculation of the disease duration. In the case of the start day and month being missing, the date will be imputed with 01 January in the calculation of the disease duration.

The disease duration will be presented in years to 1 decimal place in the listings.

The Karnofsky Performance Scale index is a semi-quantitative score ranging from 0 to 100% in intervals of 10, where 0% is death and 100% is normal (no complaints, no evidence of disease). Summary statistics for the Karnofsky Performance Scale will include n, median, minimum and maximum only.

The ITP bleeding scale will be summarized (n, median, minimum and maximum) by dose arm for each domain (SMOG).

6.3 Medical history and concomitant diseases

Medical history will be summarized for the SS by dose arm and for all subjects by MedDRA system organ class (SOC), high level term (HLT) and preferred term (PT). The listing will also include the reported condition and the start and end date (or ongoing, if applicable). Procedure history and history of thrombocytopenia will be listed separately by dose arm for the procedure reported term based on the SS.

Concomitant medical procedures performed during the study will be listed for the SS.

6.4 Past, prior, baseline and concomitant medications

Past, prior, baseline and concomitant medications will be summarized for the SS by dose arm and for all subjects by WHODD Anatomical Main Group [Level 1], Therapeutic Subgroup [Level 2] and PT.

All medications will be listed and will include coding information, reported term, dose per intake and unit, frequency, formulation, route of administration, indication, category (past/prior and concomitant/concomitant) and start and end date (or ongoing, if applicable).

6.4.1 Past medication definition

Past medications will include any medications that started and stopped prior to the first administration of UCB7665.

6.4.2 Prior medication definition

Prior medications will include any medications that started prior to the first administration of UCB7665. This includes medications that started and stopped prior to dosing (past medications) as well as those that started prior to dosing and continued after (classified as prior and concomitant medications).

6.4.3 Baseline medication definition

Baseline medications will include any medications that started prior to dosing and continued after (classified as prior and concomitant medications).

6.4.4 Concomitant medication definition

Concomitant medications will include any medication that has been taken at least once (after the first administration of UCB7665) during the Dosing Period and/or the Observation Period.

This includes medications that started prior to the dosing and continued after (classified as prior and concomitant medications) as well as any medication that started after the first administration of UCB7665 (classified as concomitant).

Any medications with missing dates and/or times will be handled as described in [Section 4.2.7](#) in order to classify them as prior and/or concomitant.

7 MEASUREMENTS OF TREATMENT COMPLIANCE

The study medication will be administered and monitored by the investigator or designee. The measured plasma concentrations will provide information regarding compliance. Any dosing deviations (eg, incomplete infusion volume administered, infusion discontinued) will be discussed at the DEM and any actions taken regarding the analyses will be documented accordingly and discussed in the CSR.

There will be no specific analysis of compliance. Exposure to UCB7665 will be presented as described in [Section 10.1](#).

8 EFFICACY ANALYSES

All analyses of the efficacy variables will be performed on the FAS. Additional outputs may be repeated for the PPS where indicated. Treatment (dose arm) assignment for efficacy analysis will be according to the actual treatment regimen.

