3.5.3 Full Analysis Set

The Full Analysis Set (FAS) will consist of all subjects who have received at least 1 infusion (full infusion) of UCB7665 and, in addition, have a Baseline and at least 1 post-Baseline measurement for platelet count (measured by ACM Global Central Laboratory).

The analysis of the PD (excluding total IgG and IgG subclasses), efficacy and immunologic variables will be performed on the FAS. Efficacy analyses will be repeated for the pharmacodynamics per protocol set (PD-PPS) where stated in the SAP.

Platelet data for subjects who have taken rescue medications (based on medical review and defined in Section 8.1.4) will only be utilized in the summary tables up to the start of these rescue medications.

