3.6 Treatment assignment and treatment groups

Treatment (dose arm) assignment for the SS, FAS, PK-PPS, PD-PPS and the PPS will be according to the planned treatment regimen (reflecting the potential DMC decisions).

In the event that the number of planned infusions in the dose arms are modified following review by the DMC, the data will be summarized based on the actual dose arms completing the study. For example, if the weekly 5x4mg/kg QWK dose arm is modified such that some subjects receive only 4 infusions, then the data will be summarized separately for this new dose regimen.

Analyses will be performed by dose arm, unless otherwise stated.

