9.3.3 Serum biomarkers

Serum safety biomarkers [REDACTED] and BAFF will be listed by dose arm and timepoint including changes from Baseline. Descriptive summaries (including n, arithmetic mean, median, SD, minimum and maximum) will be presented by dose arm and timepoint for both absolute values and changes from Baseline.

Mean and mean change from Baseline values will be plotted over time by dose arm with all dose arms overlaid on the same plot and separate plots for each variable.

Any values are that BLQ or ALQ will be handled as described in [Section 4.2.4](#).

All analyses described in this section will be performed on the FAS.

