10 SAFETY ANALYSES

All safety analyses will be presented using the SS. Listing will be presented by dose arm and subject; tabulations will be presented by dose arm and overall (AE data only), with the lowest dose per kg presented first and continuing in ascending order.

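### Efficacy is assigned by actual regimen in Section 8 but by planned regimen in Section 3.6, and serum safety biomarkers are run on the FAS although safety data belong on the Safety Set

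*SAP*

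**What the plan says.** **Arm assignment.** For the SS, FAS, PK-PPS, PD-PPS and PPS, SAP Section 3.6 states that assignment "will be according to the planned treatment regimen (reflecting the potential DMC decisions"). Section 8 places efficacy on the FAS, with repeats on the PPS, and adds: "Treatment (dose arm) assignment for efficacy analysis will be according to the actual treatment regimen". Section 3.6 also covers a DMC change to the number of planned infusions, in which case "the data will be summarized based on the actual dose arms completing the study". Section 3.1 repeats this, and Section 10.1 treats a DMC-modified regimen as a new arm.

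**Serum safety biomarkers.** Section 2.2.1.2 lists serum biomarkers among the other safety variables, and Table 3-1 puts serum safety biomarkers under safety data. Section 3.5.2 says that the SS is used for safety data and admits full or partial infusions. Section 10 says "All safety analyses will be presented using the SS". Section 9.3.3, which covers these biomarkers, says "All analyses described in this section will be performed on the FAS". The FAS consists of "all subjects who have received at least 1 infusion (full infusion) of UCB7665" who also have a Baseline and at least one post-Baseline central platelet count (Section 3.5.3).

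**Two smaller items.** Section 9.3.5 puts cytokines on the FAS; post-dose samples come from subjects with severe infusion reactions or from a DMC or sponsor request. Section 3.5.3 says "Efficacy analyses will be repeated for the pharmacodynamics per protocol set (PD-PPS) where stated in the SAP", whereas Section 8 names the PPS.

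**The concern.** A FAS subject has two arm rules. They agree for anyone who completes the planned regimen and can disagree for anyone who does not. Efficacy is summarised and tested within arm, so the rule decides which subjects enter each mean, responder rate and t-test, and which group they join in the log-rank comparison. If the two rules are programmed as written, efficacy and safety tables could carry the same arm label over different subjects.

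The biomarker conflict concerns who is counted. A subject whose only infusion was stopped partway, perhaps for a reaction, is a treated subject for safety purposes. That subject would still be absent from the summaries of a variable that the SAP itself classes as safety.

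**Working it through.** **1. The plan's own figure.** Section 2.4 claims power above 80% for the responder endpoints with 15 subjects, a true rate of 50% and at most 15% without benefit. Tests are 1-sided at 5% (Section 3.1). Exact binomial check:

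- P(X ≥ 5 | n = 15, p = 0.15) = 0.0617, above 0.05.
- P(X ≥ 6 | n = 15, p = 0.15) = 0.0168, so success needs 6 or more responders.
- P(X ≥ 6 | n = 15, p = 0.50) = 0.849.

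The claim is reproduced. It presumes that all 15 subjects are counted in the arm; the point below rests on the text and not on this figure.

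**2. The two assignment rules, case by case.**

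| FAS subject | Section 3.6 (planned) | Section 8 (actual, read literally) |
|---|---|---|
| Completes the planned infusions | Planned arm | Same arm |
| Regimen changed by the DMC | New, modified arm | Same modified arm |
| Stops early individually | Planned arm | No arm defined |

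Only the third row conflicts. Sections 3.1, 3.6 and 10.1 create a new column only after a DMC change, so the literal reading sends an individual early stopper to a column that does not exist. If one were created with fewer than 3 subjects, Section 3.1 would allow only n, minimum and maximum. Section 3.1 provides an overall presentation for adverse events only; for efficacy, the total in the time-to-response counts (Section 8.1.3.2) is an exception.

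FAS entry needs one full infusion, and Arms 4 and 5 have one planned dose. Barring a dosing error, their FAS subjects received the full regimen. The assignment conflict therefore matters in Arms 1 to 3.

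**3. What the third row could change.** Section 8.1.3.1 runs the t-test only in arms with at least 10 subjects. The number moved that would cancel the test is arm size minus 9:

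- Arms 1 and 2 (15 planned): 15 − 9 = 6.
- Arm 3 at its maximum of 12: 12 − 9 = 3.
- Arm 3 at 10: 10 − 9 = 1.

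The direction of any shift depends on who stops. As an invented example, take 6 responders among 15 (6/15 = 40.0%) and move two subjects out:

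- Neither had responded: 6/13 = 46.2%.
- Both had responded: 4/13 = 30.8%.

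This shows only that the sign is unknown. The SAP gives no expected number of early stoppers.

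**4. SS against FAS for the safety biomarkers.**

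| Requirement | SS | FAS |
|---|---|---|
| Infusion | At least one, full or partial | At least one full |
| Baseline central platelet count | No | Yes |
| Post-Baseline central platelet count | No | Yes |

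In Arms 1 to 3, a subject fails the infusion condition only if no infusion was ever completed; a reaction after one full infusion does not exclude anyone. In Arms 4 and 5, any incomplete infusion does. Each such subject is 1/12 = 8% to 1/6 = 17% of an arm of 12 to 6. That is a share per subject and says nothing about frequency.

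**5. What is not lost.** Section 9.3 puts its listings on the SS, and Section 10 puts adverse events, laboratory data, vital signs and ECG on the SS. The gap is in the biomarker summary tables and figures.

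**The case against.** The best defence on assignment is that actual in Section 8 means the DMC-modified regimen. Section 3.6 uses the word that way ("the data will be summarized based on the actual dose arms completing the study"), and the Amendment 1 log shows the Section 8 sentence arriving together with the DMC wording in 3.6. Other rules also assume that stoppers remain in their FAS arm. The PPS separately requires all planned infusions, Section 8.1.3.2 censors at withdrawal, Section 8.1.1 drops early withdrawals from the AUEC only, and Section 7 sends dosing deviations to the data evaluation meeting. This may well be the intent, and no text deletes a stopper. But Section 8 does not say so, and its word is the opposite of the one in 3.6, so the conflict stands.

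On biomarkers, Section 4.2.4 groups serum biomarkers with immunological data, which Section 9.3 puts on the FAS. But 4.2.4 governs values outside the quantification limits, while Section 2.2.1.2 and Table 3-1 classify the safety biomarkers as safety data.

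A reader might infer more than the SAP supports:

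- **Efficacy is biased upward.** This needs stoppers to respond less often, which nothing in the SAP establishes.
- **Reaction cases vanish from the safety evaluation.** The adverse event tables and the listings keep them.
- **The cytokine set is a contradiction of the same kind.** Cytokines are immunological variables (Section 2.2.4), placed on the FAS by stated rule, and any summary needs at least 5 subjects with post-dose data. Moving them is a sensible alignment only. The FAS rule is not uniform, though, since Section 9.3.4 analyses immunological variables on the SS.
- **Efficacy would be rerun on an IgG-based set.** The PD-PPS sentence applies only where the SAP states such a repeat, and no efficacy section does.
- **Safety should be assigned by dose received.** That would overturn 3.6 as a matter of preference and could recreate the mismatch between efficacy and safety columns.

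**Conclusion.** Two contradictions in the current text hold and should be corrected.

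First, Sections 3.6 and 8 give different arm rules for the same sets. On the literal reading, individual early stoppers in Arms 1 to 3 have no defined efficacy column. The effect on estimates is of unknown size and direction, and it disappears if actual was meant as DMC-modified.

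Second, Section 9.3.3 uses a set that conflicts with the SAP's own classification of the safety biomarkers. It leaves out of the summaries any subject who never completed an infusion or lacks a required platelet count. The exposure is greatest in Arms 4 and 5. The primary safety variable is unaffected.

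The cytokine set and the PD-PPS wording are minor alignments.

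**What to change.** 1. In Section 8, replace the assignment sentence with the Section 3.6 rule: planned regimen, including any DMC-modified regimen, with individual early stoppers kept in their planned arm.
2. In Section 9.3.3, run the serum safety biomarkers on the SS, and make the general FAS statement in Section 9.3 consistent with that. BAFF, an immunological variable in Section 2.2.4, can stay on the FAS if the two are named separately.
3. As minor alignments, summarise post-dose cytokines (Section 9.3.5) on the SS, since they are collected mainly after severe infusion reactions, and change PD-PPS to PPS in the efficacy sentence of Section 3.5.3.

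Leave safety assignment as in Section 3.6. The cost is a few sentences and the matching population flags in the table shells. No new data are needed, and no figure in Section 2.4 changes.

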8.1 Platelets

All efficacy analyses are based on platelet count measured by ACM Global Central Laboratory. Measurements of platelet count obtained by the local laboratory will be listed and summarized as part of the safety laboratory data. These are not included in the analyses described in the sections below. All tabulations and mean figures will be presented for both the FAS and the PPS unless otherwise stated. Median figures and individual figures will be presented for the FAS only. In case rescue medications are taken, only the platelet data up to the start date of rescue medication will be utilized for the summary tables (refer to [Section 8.1.4](#)). In case prohibited medications

affecting platelets are taken, only the platelet data up to the start date of prohibited medication will be utilized for the summary tables for the PPS (refer to Section 3.4). Listings will contain all the data but a footnote will be included indicating the patients for which some data has been excluded from the summary tables. In case of partial dates, the imputation rules for partial dates described in Section 4.2.7 will be applied.

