8.1.2 Presentation of results

The individual platelet measurements will be listed by dose arm and visit including changes from Baseline (Day 1, pre-dose). Descriptive summaries (including n, arithmetic mean, median, SD, minimum and maximum) will be presented by dose arm and scheduled visit for both absolute values and changes from Baseline based on the FAS only. Summary tabulations by dose arm will be repeated for the subgroups defined in [Section 4.8](#) (based on the FAS only too).

In addition, a separate listing and summary will be presented (by visit, where applicable) including the following:

- *Response by visit and over all visits
- Time to Response
- Duration of Response
- *Complete Response by visit and over all visits
- Time to Complete Response
- Duration of Complete Response
- *Platelet Count $\geq 50 \times 10^9/L$ by visit and over all visits
- Time to Platelet Count $\geq 50 \times 10^9/L$
- Duration of Platelet Count $\geq 50 \times 10^9/L$
- Maximum value
- Maximum Increase from Baseline
- Baseline-corrected AUEC

*All the above variables will be included in the listing. The number and percentage of responders (for variables denoted with an asterisk) will be tabulated separately as described in [Section 8.1.3.3](#).

Summary tabulations by dose arm will be repeated for the subgroups defined in [Section 4.8](#) (based on the FAS only).

Mean and mean change from Baseline platelet values will be plotted versus scheduled visit by dose arm with all dose arms overlaid on the same plot. Similar plots will be provided for response rate over time (response, complete response and platelet count $\geq 50 \times 10^9/L$). Mean median, mean change and median change from Baseline total IgG results will be plotted over time by dose arm with all dose arms overlaid on the same plot.

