Individual platelet and total IgG (including IgG subclasses, measured by ACM Global Central Laboratory) concentrations will be displayed graphically over time (Day 1 to Day 85 for Dose Arm 1; Day 1 to Day 71 for Dose Arm 2; Day 1 to Day 64 for Dose Arm 3 and Day 1 to Day 57 for Dose Arms 4 and 5) for each subject (linear scale). The platelet and total IgG concentrations will be overlaid on the same plot (discrete y-axes) with separate plots for each subject (2 lines per plot). Additional plots will be presented with the platelet and IgG subclasses overlaid on the same figure (5 lines per plot). All plots will include a vertical reference line to indicate when the last dose was administered for each subject. The mean (and median in a separate plot) change from baseline in platelet and the mean (median) change from baseline in total IgG concentrations will be overlaid on the same plot (discrete y-axes) with separate plots for each dose arm (2 lines per plot).

In addition scatter plots will be presented showing the Maximum value for platelet count versus the corresponding total IgG i.e., the value of total IgG at the time of the Maximum platelet value. All subjects will be included on the same plot with distinct symbols to distinguish the dose arms. This plot will be repeated for the Maximum platelet value versus percentage change in total IgG i.e., the percentage change from Baseline in total IgG at the time of the Maximum platelet value.

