8.1.3.2 Analysis of time to response

The time to first response will be analyzed with the log-rank test and displayed using Kaplan-Meier curves.

Kaplan-Meier curves will be presented for the variables Time to Response, Time to Complete Response, and Time to Platelet Count $\geq 50 \times 10^9/L$. Descriptive statistics will include the p-value for the log-rank test for the equality over dose arms. The point estimate for the median number of days to response with 90% CIs will be given if estimable. Further a summary including the number and percent of censored subjects, the number of responders and total subjects by dose arm and in total will be given.

For the purpose of the analysis subjects with no response will be censored at the end of the study or at the date of withdrawal.

Analyses will be performed for the FAS and repeated for the PPS.

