8.1.3.3 Analysis of responder rate

The number and percentage of subjects achieving a Response, Complete Response and Platelet Count $\geq 50 \times 10^9/L$ will be summarized by dose arm at each scheduled post-Baseline visit. The 90% CI for the percentage of responders will be included, calculated using a Wilson approximation. The tabulation will also include an overall summary (across all visits) of the number and percentage of subjects achieving a Response, Complete Response and Platelet Count $\geq 50 \times 10^9/L$ at any time during the study. For the purpose of the tabulation the lower and upper 90% CI for the percentage of subjects will be truncated at 0 and 100% respectively.

In addition the percentage of subjects achieving a Response, Complete Response and Platelet Count $\geq 50 \times 10^9/L$ will be plotted at each post-Baseline visit. Separate plots will be presented for each response type with all dose arms overlaid on the same plot.

Analyses will be performed for the FAS and repeated for the PPS. Summary tabulations by dose arm will be repeated for the subgroups defined in [Section 4.8](#) (based on the FAS only). Percentage of days without bleeding will also be described by dose arm for each type of response (response, complete response and platelet Count $\geq 50 \times 10^9/L$). Percentage of days without bleeding is calculated using the following formula:

$$\frac{((N \text{ of visits with a SMOG score} - N \text{ of these visits where bleeding occurred}) / N \text{ of visits with a SMOG score}) \times 100$$

In case rescue medications are taken, only the data up to the start date of rescue medication will be utilized for the summary tables. Listings will contain all the data but a footnote will be included indicating the patients for which some data has been excluded from the summary tables. In case of partial dates, the imputation rules for partial dates described in [Section 4.2.7](#) will be applied.

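### The platelet rescue cut-off is written only for the summary tables, so the Kaplan-Meier curves and the mean, response-rate and scatter figures can count post-rescue rises as drug response

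*SAP*

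**What the plan says.** The cut-off appears in several places, each time tied to one kind of output. Section 8.1: "only the platelet data up to the start date of rescue medication will be utilized for the summary tables". Section 3.5.3: platelet data of rescued subjects "will only be utilized in the summary tables up to the start of these rescue medications". Section 8.1.3.3: "only the data up to the start date of rescue medication will be utilized for the summary tables". Section 8.2.1.1 has the same limit twice, and section 9.2.2 has it for IgG. The only other output with a rule is the listings: "Listings will contain all the data but a footnote will be included".

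Section 8.1.4 defines rescue as platelet substitution or commercial IVIg, and adds plasma exchange (PLEX), dexamethasone and rituximab for analysis.

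The time-to-response analysis has no rescue rule. In 8.1.1 the event is the first achievement of response during the study, and unscheduled counts are allowed. In 8.1.3.2, "subjects with no response will be censored at the end of the study or at the date of withdrawal". The figures have none either. In 8.1.2, "Mean and mean change from Baseline platelet values will be plotted versus scheduled visit by dose arm", and "scatter plots will be presented showing the Maximum value for platelet count versus the corresponding total IgG". The maximum is taken over all study visits (8.1.1). Section 8.1.3.3 also plans plots of the response percentages by visit.

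**The concern.** Platelet substitution adds platelets directly, and the other listed agents are treated in the SAP as enough of a disturbance to justify cutting the data. If the cut reaches only the tables, a platelet rise after rescue can still appear as a response to UCB7665 on the curves and in the group figures. Two outputs for the same endpoint could then disagree within one report, and two programmers could each follow the SAP and produce different results.

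The scatter plots have a second problem. The count at the maximum may follow IVIg, and the total IgG paired with it may then include infused immunoglobulin. IgG reduction is the drug's measured pharmacodynamic effect (2.1.2), and its relation to platelet change is an exploratory objective (2.1.3), so such a point would distort what the plot is meant to show.

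**Working it through.** **1. Does *summary tables* include figures?** The paragraph in 8.1 that states the cut-off also says "All tabulations and mean figures will be presented for both the FAS and the PPS unless otherwise stated", and then treats median and individual figures separately. The SAP therefore distinguishes tabulations from figures just before limiting the rule to tables.

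**2. One subject through the rules.** Take a subject with no response before rescue, whose first count meeting the definition comes after it.
- Response table (8.1.3.3): post-rescue counts are dropped, so non-responder.
- Kaplan-Meier curve (8.1.1 and 8.1.3.2): rescue neither ends follow-up nor disqualifies a later count, so an event on the later date.
- Response-rate plot (8.1.3.3): no cut-off stated, so a responder at that visit, although the table of the same percentages is cut.
- Mean plot and maximum scatter (8.1.2): no cut-off stated, so the post-rescue count enters.

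**3. The plan's own figure.** Section 2.4 claims power above 80% for a 50% response rate against 15% with 15 subjects. The exact binomial rule at one-sided 5% is at least 6 of 15 (exact alpha 1.7%; 5 of 15 would give 6.2%), and its power is 84.9%. The claim reproduces. It concerns the number of responders, whose table is already cut, so this point leaves it intact.

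**4. Size on the curve.** Arm sizes 6, 12 and 15 come from 2.3. If no one is censored earlier and the subject would otherwise stay a non-responder, one extra event adds 1/n: 1/6 = 16.7, 1/12 = 8.3 and 1/15 = 6.7 percentage points. With earlier censoring the step would differ.

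**5. Size on the mean plot.** Assume a post-rescue count of 200, Baseline 25, and the other n − 1 subjects at the planning change in 2.4 (100 − 25 = 75). The rescued subject's change is 200 − 25 = 175.
- Cut-off applied: the value is excluded and not imputed (4.2.1), so the mean change is 75.
- Not applied: [(n − 1) × 75 + 175]/n = 75 + 100/n.
- Shift: 100/6 = 16.7, 100/12 = 8.3, 100/15 = 6.7, or about 17, 8 and 7 x10^9/L.

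**6. The log-rank test, if run on uncut data.** This simulation used two arms of 15, 30% drug response in both, response times uniform over days 3 to 57, rescue uniform over days 7 to 40, 80% of rescued subjects crossing five days later, nominal 5% and 4,000 runs. The cut version censors at rescue.

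| Rescue shares | Post-rescue rises counted | Data stopped at rescue |
|---|---|---|
| 10% v 10% | 5.2% | 4.4% |
| 30% v 10% | 10.0% | 5.0% |
| 40% v 10% | 16.1% | 5.6% |

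All rescue and timing inputs are assumptions, and the planned test runs over all dose arms rather than two. The distortion comes mainly from unequal rescue use.

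**The case against.** The best defence is that the rule opens section 8.1 and so governs everything below it, and that *summary tables* was meant only as the opposite of listings. The amendment history, read solely as evidence of intent, agrees. The wording added under Amendment 1 had no output limit, and Amendment 2 brought in the limit together with the sentence preserving full listings.

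Much of this stands. A reader might infer that no statistical test is protected, but the document does not support that. The t-test result for maximum increase is to be tabulated (8.1.3.1). The log-rank p-value, median and counts of responders and censored subjects are described as descriptive statistics and a summary (8.1.3.2), so they will probably be tables too. Nor is it certain that the report will show two sets of responders; that follows from the literal reading only.

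A reader might also put the mean shift at (200 − 25)/n = 29, 15 and 12. That treats the rescued subject as otherwise contributing zero change, whereas under the cut-off the value is simply absent. And the SAP states no trigger for rescue, so it does not establish that rescue was given because UCB7665 failed.

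The defence does not repair 8.1.3.2, which names its censoring points without rescue, or the figures. If the Kaplan-Meier table is cut and the curve is not, the inconsistency falls within a single endpoint.

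**Conclusion.** The gap is real for the Kaplan-Meier event and censoring rule and for the mean, response-rate and maximum-platelet scatter figures. For tabulated results it is at most an ambiguity. Where post-rescue counts enter because they are high, the error favours the drug. One subject could matter in arms this small, by the amounts worked out above, but those amounts rest on an assumed post-rescue count, no earlier censoring and other subjects at the planning change. How many subjects were rescued is not stated, so the actual effect may be nil.

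This should be fixed but is not critical. The trial is open-label Phase 2, its primary objective is safety, the dose-arm decisions rest on safety data, and the response tables already carry the cut-off.

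**What to change.** - In 3.5.3, 8.1, 8.1.3.3 and 8.2.1.1, replace the limit to summary tables with wording that covers all platelet summaries, statistical tests, Kaplan-Meier analyses and mean, median, response-rate and scatter figures.
- In 9.2.2, apply the same cut-off to the IgG values paired with platelet counts in the scatter plots.
- In 8.1.3.2, state that only pre-rescue counts can be an event and that a subject rescued without an earlier response is handled as a non-responder. Censoring at rescue is the alternative, but non-response matches the 8.1.3.3 table and avoids censoring that may depend on outcome.
- Use one rule for counts on the rescue start date. The last paragraph of 8.2.1.1 excludes that date; 8.1 and 8.1.3.3 do not say.
- Keep post-rescue counts only in listings and individual plots, visibly marked.

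The cost is SAP wording and wider use of an exclusion flag the tables already need; no new data are required. Curves may look slightly less favourable. Mean plots would lose rescued subjects' later values, which can itself be selective, so the number contributing at each visit should be shown.
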